3.3.1. Study Treatments

Treatment will be administered in 28-day cycles. Glasdegib will be administered at the starting dose of 100 mg orally once/day and continuously in combination with azacitidine.

Safety Lead-In Cohort

The safety lead-in cohort has been completed.

- All patients will be administered glasdegib, 100 mg orally once/day and continuously;
- Azacitidine will be administered SC at the starting dose of 75 mg/m²/day on a continuous schedule from Day 1 to Day 7 of each cycle (Schedule 1). Patients with >30% BM blasts OR a rapidly progressive increase in the proportion of BM blasts at any point during the course of treatment must discontinue the study drug combination and enter follow up.

Expansion

- All patients will be administered glasdegib 100 mg orally once daily and continuously;
- Azacitidine will be administered per local label or per the Investigational Product Manual (or SPC). Azacitidine may be administered by SC injection or IV infusion at the starting dose of 75 mg/m²/day for 7 days every 28 days. Alternate dosing schedules to administer the 7 doses to accommodate patient and treatment center availability are allowed.

Since responses to azacitidine may require 4-6 cycles of administration to emerge, treatment with the study drug combination should be continued for at least 6 cycles, or until death, unacceptable toxicity, or patient refusal whichever occurs first. If documentation of disease progression occurs within the first 6 cycles of study treatment the patient **SHOULD NOT** be withdrawn from study treatment if, in the Investigator's judgment, the patient is still likely to receive clinical benefit. Treatment with the study drug combination should be continued beyond 6 cycles of treatment until objective disease progression or relapse, unacceptable toxicity, patient refusal or death, whichever occurs first. Treatment should also be continued beyond 6 cycles if patients demonstrate reasonable evidence of clinical benefit, defined as HI or better in patients enrolled into the safety LIC, SD + HI or better in MDS patients enrolled to the expansion, and not meeting the criteria for disease progression for AML patients enrolled into the expansion.

If glasdegib is permanently discontinued for reasons other than objective disease progression, patient refusal, or consent withdrawal, single-agent treatment with azacitidine may be continued if, in the Investigator's judgment, a clinical benefit has been observed and following discussion between the Investigator and Sponsor.

In cases of unacceptable toxicity or pregnancy, the patient must be withdrawn from study drug combination and entered into the follow-up phase.

When study treatment with both drugs (glasdegib and azacitidine) is permanently discontinued, patients will enter into the follow-up phase. Patients receiving at least one dose of study treatment will be followed up for survival for up to 2 years from the first visit of the last patient enrolled in the expansion component of the study, or until death, lost to follow-up, or consent withdrawal.

3.3.2. Study Assessments Summary

Patients will be followed for efficacy throughout the study by means of bone marrow aspirates. Following study entry, bone marrow biopsies will only be required if adequate bone marrow aspirates are not obtained. A CR or PR response needs to be confirmed at least 4 weeks following the BM evaluation by assessing the stability of improved counts on PB, an additional bone marrow confirmatory specimen is not required (applies to all patients in the safety LIC and only MDS patients in the expansion component).

CCI [REDACTED] Transfusional support (red blood cells and platelets) will also be recorded. Timely and complete (bone marrow AND peripheral blood counts) disease assessments at screening and during the study, whenever clinically indicated, are essential. Failure to perform any of the required disease assessments will result in the inability to determine disease status for that time point and may weaken the conclusions of the study.

Safety assessments (laboratory, instrumental and clinical) and PK assessments will be performed regularly during the active treatment period in both components of the study.

DDI assessments were performed in the safety LIC only.

CCI [REDACTED]

Please refer to the [Schedule of Activities for the Safety Lead-in Cohort](#) and the [Schedule of Activities for the Expansion: MDS and AML Patients](#) for a complete list of assessments to be performed on patients in the study.

4. PATIENT SELECTION

This study can fulfill its objectives only if appropriate patients are enrolled. The following eligibility criteria are designed to select patients for whom protocol treatment is considered appropriate. All relevant medical and non-medical conditions should be taken into consideration when deciding whether this protocol is suitable for a particular patient. These criteria must also be met prior to dosing on Cycle 1 Day 1. No exceptions will be granted.

4.1. Inclusion Criteria

Patient eligibility must be reviewed and documented by an appropriate member of the investigator's study team before patients are included in the study.

Patients must meet all the following inclusion criteria to be eligible for enrollment into the study:

4.1.1. Safety Lead-in Cohort

The safety lead-in cohort has been completed.

1. Morphologically confirmed diagnosis of one of the following:
 - a. MDS according to the WHO 2008 classification ([Appendix 1](#)), and bone marrow blasts $\geq 5\%$;
 - b. AML with 20-30 % BM blasts and multi-lineage dysplasia, according to WHO 2008 classification([Appendix 1](#)), WBC $< 20 \times 10^9/L$; CMML according to the WHO 2008 classification ([Appendix 1](#)) and BM blasts between 10% - 19% and WBC $< 13 \times 10^9/L$.
2. MDS patients must have Intermediate-2 (1.5 to 2.0 points) or High-Risk (≥ 2.5 points) disease according to the International Prognostic Scoring System 1997 (IPSS).
3. MDS patients must have normal levels of vitamin B12 within the institutional range of normal as determined within 28 days of study entry.
4. AML patients with 20-30% BM blasts and multi-lineage dysplasia, must have stable blast counts per Investigator's judgment.
5. Clinical indication for treatment with azacitidine for MDS, AML or CMML.
6. Eastern Cooperative Oncology Group (ECOG) Performance Status ≤ 2 . See [Appendix 9](#).
7. ≥ 18 years of age.
8. Adequate Renal Function:
 - Serum creatinine ≤ 1.5 x upper limit of normal (ULN);

OR

 - Estimated creatinine clearance ≥ 60 ml/min (calculated using the standard method for the institution).
9. Adequate Liver Function:

- Total serum bilirubin ≤ 1.5 x ULN (unless the bilirubin is principally unconjugated and there is strong suspicion of sub-clinical hemolysis or the patient has documented Gilbert's disease);
 - Aspartate transaminase (AST) and Alanine transaminase (ALT) ≤ 2.5 x ULN;
 - Alkaline phosphatase ≤ 2.5 x ULN.
10. Serum amylase or lipase < 1.5 x ULN.
 11. Serum or urine pregnancy test (for female patients of childbearing potential) with a minimum sensitivity of 25 IU/L or equivalent units of human chorionic gonadotropin (HCG) negative at screening.
 12. Male and female patients of childbearing potential and at risk for pregnancy must agree to use two highly effective method(s) of contraception throughout the study and for 90 days after the last dose of azacitidine and the last dose of glasdegib or placebo, whichever occurs later.
 13. Female patients who are not of childbearing potential (ie, meet at least 1 of the following criteria):
 - a. Have undergone a documented hysterectomy and/or bilateral oophorectomy;
 - b. Have medically confirmed ovarian failure; or
 14. Achieved postmenopausal status, defined as follows: cessation of regular menses for at least 12 consecutive months with no alternative pathological or physiological cause; status may be confirmed by having a serum follicle stimulating hormone (FSH) level within the laboratory's reference range for postmenopausal women.
 15. Evidence of a personally signed and dated informed consent document indicating that the patient (or a legally acceptable representative) has been informed of all pertinent aspects of the study.
 16. Patients who are willing and able to comply with scheduled visits, treatment plans, laboratory tests and other procedures (including BM assessments).

4.1.2. Expansion

Patients must meet all the following inclusion criteria to be eligible for enrollment into the expansion cohorts:

1. Patients must have previously untreated MDS or AML according to the WHO 2016 classification. ([Appendix 17](#)).
 - a. The following AML patients will be included:

- AML arising from MDS or another antecedent hematologic disease (AHD).
 - AML after previous cytotoxic therapy or radiation (secondary AML).
- b. MDS patients must have Intermediate (>3 to 4.5 points), High-Risk (>4.5 – 6) or Very High-Risk (>6 points) disease according to the Revised International Prognostic Scoring System 2012 (IPSS-R). ([Appendix 10](#)).
- CMML patients according to the WHO 2016 classification ([Appendix 17](#)) are included in the MDS cohort.
 - MDS/MPN, unclassifiable patients according to the WHO 2016 classification ([Appendix 17](#)) are included in the MDS cohort.
2. Clinical indication for treatment with azacitidine for MDS or AML.
3. ≥ 18 years of age.
4. Adequate organ function as defined by the following:
- Total serum bilirubin ≤ 2 x ULN (unless the bilirubin is principally unconjugated and there is strong suspicion of sub-clinical hemolysis or the patient has documented Gilbert's disease);
 - Aspartate transaminase (AST) and Alanine transaminase (ALT) ≤ 3 x ULN, excluding patients with liver function abnormalities due to underlying malignancy;
 - Estimated creatinine clearance ≥ 30 mL/min as calculated using the standard method for the institution.
5. Serum or urine pregnancy test (for female patients of childbearing potential) with a minimum sensitivity of 25 IU/L or equivalent units of human chorionic gonadotropin (HCG) negative at screening.
6. Male and female patients of childbearing potential and at risk for pregnancy must agree to use at least (1) highly effective method(s) of contraception throughout the study and for 180 days after the last dose of azacitidine and the last dose of glasdegib, whichever occurs later.
7. Female patients who are not of childbearing potential must meet at least 1 of the following criteria:
- a. Have undergone a documented hysterectomy and/or bilateral oophorectomy;
 - b. Have medically confirmed ovarian failure; or

- c. Achieved postmenopausal status, defined as follows: cessation of regular menses for at least 12 consecutive months with no alternative pathological or physiological cause; status may be confirmed by having a serum follicle stimulating hormone (FSH) level within the laboratory's reference range for postmenopausal women.

All other female patients (including female patients with tubal ligations) are considered to be of childbearing potential.

8. Evidence of a personally signed and dated informed consent document indicating that the patient (or a legally acceptable representative) has been informed of all pertinent aspects of the study.
9. Patients who are willing and able to comply with scheduled visits, treatment plans, laboratory tests and other procedures (including BM assessments).

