In the expansion component of this study, patients with Intermediate, High, or Very High risk MDS according to IPSS-R and AML patients who are not candidates for intensive chemotherapy (WHO 2016) will be enrolled. CMML patients and patients with unclassifiable MDS/MPN are eligible for enrollment into the MDS cohort. Based on the results of the AZA-AML trial, the azacitidine label was expanded in 2009, making azacitidine a standard of care treatment in elderly AML patients unable to tolerate intensive therapies. This historical data, coupled with the preliminary efficacy data from the safety LIC of the current study warrants further investigation of azacitidine's benefit in a larger AML population. Since several prognostic and classification systems were recently updated, the following will be implemented in the expansion component of the study to make it more contemporary: IPSS-R and the WHO 2016 classification system will be applied to the MDS patients and the updated 2017 ELN risk stratification and updated response categories and the revised WHO 2016 classification system will be applied to the AML patients.

Given the central role that Hh signaling plays in cellular differentiation through modulating both the leukemia stem cells (LSC) population and the surrounding stromal environment, Hh inhibition in combination with HMAs represents a mechanistically attractive approach for the elimination of the LSC population while targeting the gene expression deregulation involved in the pathway development in patients with Higher-Risk MDS, AML, and CMML.

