7.7. Efficacy Assessments

7.7.1. Response Criteria

Disease response, measured from baseline through the End of Treatment, will be evaluated using IWG Modified Response Criteria ([Appendix 2](#)) for all patients in the Safety Lead-In cohort and for the MDS patients in the Expansion. The 2017 ELN Response Criteria will be applied to all AML patients in the Expansion ([Appendix 11](#)).

CR with partial hematologic recovery (CRh) will be assessed for the AML Expansion Cohort. CRh is defined as CR but with ANC $>$ 0.5x10⁹/L and platelets $>$ 50x10⁹/L.

CCI

CCI

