9.2. Analysis Populations

9.2.1. Full Analysis Set (FAS)

The FAS will include all enrolled patients in the respective cohort (LIC, expansion MDS, and expansion AML cohort separately), who received at least one dose of any study treatment (glasdegib or azacitidine). This will be the primary analysis population for evaluating efficacy endpoints and patient characteristics.

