9.7. Interim Analyses

9.7.1. Futility Analyses

A Bayesian decision rule (Section 3.3) will be used to continuously monitor CR rate without holding enrollment in the expansion component to allow early stopping of the study for futility. The decision rule is to stop enrollment for a specific expansion cohort if the posterior probability of the CR rate in study treatment is no more than 0.2 higher than historical azacitidine is greater than 95% in an expansion cohort, ie, $\Pr(\text{glasdegib+Aza response} < \text{historical Aza response} + 0.2) > 0.95$. The prior distribution assumptions for the Bayesian model are as follow: for MDS cohort, we assume a prior distribution of Beta(1,6) for the study treatment (based on data from MDS patients accumulated in the safety LIC [1 out of 7 MDS patients achieved CR]), and a prior distribution of Beta(15,75) by discounting historical CR rate by half (AZA 001 trial); for the AML cohort, a prior distribution of Beta(4,4) for the study treatment (based on pooled data on AML patients from the B1371003 study [1 out of 4 AML patients achieved CR] and the LIC [3 out of 4 AML patients achieved CR]), and a prior distribution of Beta(23.5,97) by discounting historical CR rate by half.⁵⁷ The Multic Lean software (Version 2.1.0) developed by MD Anderson Cancer Center is used (https://biostatistics.mdanderson.org/softwaredownload/SingleSoftware.aspx?Software_Id=12), which properly models variability in historical control that is more often than not ignored. Stopping for toxicity is not modeled.

The Bayesian decision rule applies once the minimum number of patients (ie, 10) in each expansion cohort has achieved the required follow-up duration (ie, 28 weeks for the expansion MDS cohort and 24 weeks for the expansion AML cohort). The enrollment to the respective expansion cohort will be stopped if the minimum number of responders in that expansion cohort is not achieved (Table 8 for expansion MDS cohort, and Table 9 for expansion AML cohort in Section 3.3). For instance, if there are no more than 4 responders in the first 17 patients who have achieved 28 weeks follow-up, the enrollment into the expansion MDS cohort should be stopped for futility.

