Appendix 2. IWG Criteria: Response Criteria and Progression Definitions for Myelodysplasia***

Response Criteria (responses CR, PR, mCR must last at least 4 weeks)	Peripheral Blood				Bone Marrow Blasts (BMB) (%)	Other
	Hgb(g/dL)	Neutrophils (L)	Platelets (L)	Blasts (%)		
Complete Remission (CR)**	≥11	≥1 x 10 ⁹	≥100 x 10 ⁹	0	≤5	Normal maturation of all cell lines, note if has persistent dysplasia
Partial Remission (PR)**					Decreased by ≥50% but still >5%	All CR criteria if abnormal before treatment except BMB
Marrow CR (mCR)	If hematologic improvement (HI) response, note in addition to Marrow CR				≤5% & decreased by ≥50%	
Stable Disease*						Failure to achieve PR & no evidence of progression*
Failure						Death, or disease progression: worsening cytopenia, increase in % BM blasts, progression to a more advanced MDS FAB subtype
Relapse after (m)CR or PR					ICH	At least one of the following: Return to pre-treatment BMB % Decrement of ≥50% from maximum remission/response levels in granulocytes or platelets Reduction in Hgb ≥1.5g/dL or transfusion dependence

*SD must last >8 weeks but response is documented regardless of duration.

**Stability of the improved counts is sufficient to define CR or PR without the need to repeat a second BM.

***This criteria will be applied to MDS patients enrolled in the Safety Lead-In and Expansion components of the study and patients with AML with 20-30% blasts and multi-lineage dysplasia and CMML without proliferative disorder enrolled into the Safety Lead-In component of the study.

Additional Response Criteria for Myelodysplasia***

Cytogenetic Response Complete Partial	Disappearance of chromosomal abnormality with no appearance of new ones $\geq 50\%$ reduction of chromosomal abnormality
Disease Progression For patients with % blasts at screening: <5% bone marrow blasts 5-10% bone marrow blasts 11-20% bone marrow blasts 21-30% bone marrow blasts For all categories, any of:	$\geq 50\%$ increase to >5% bone marrow blasts $\geq 50\%$ increase to >10% bone marrow blasts $\geq 50\%$ increase to >20% bone marrow blasts $\geq 50\%$ increase to >30% bone marrow blasts At least 50% decrease from maximum remission/response in granulocytes or platelets Reduction in Hgb by ≥ 2 g/dL Transfusion dependence

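### The expansion MDS cohort counts CMML and unclassifiable MDS/MPN in the primary CR rate, with no check that CR was absent at screening and a historical control that only partly matches

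*Protocol*

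**What the plan says.** **Eligibility.** Expansion criterion 1b (Protocol 4.1.2) includes "CMML patients according to the WHO 2016 classification" in the MDS cohort, and MDS/MPN-U as well. Protocol 1.2.3 repeats this: "CMML patients and patients with unclassifiable MDS/MPN are eligible for enrollment into the MDS cohort". No blast or white-cell limit is attached. The lead-in cohort did limit CMML (Protocol 4.1.1): "BM blasts between 10% - 19% and WBC" below 13 x 10^9/L. Criterion 2 of the expansion asks for "Clinical indication for treatment with azacitidine for MDS or AML".

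**Analysis population.** Protocol 9.2.1: "The FAS will include all enrolled patients in the respective cohort", provided they received at least one dose. This is the population for the primary CR rate (Protocol 9.3.1, SAP 8.2.1).

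**Response criteria.** Protocol 7.7.1 applies the IWG 2006 criteria "for all patients in the Safety Lead-In cohort and for the MDS patients in the Expansion". The footnote to Protocol Appendix 2 names CMML only as "CMML without proliferative disorder enrolled into the Safety Lead-In component of the study". The footnote to SAP Appendix 2 also covers non-proliferative CMML, but without restricting it to the lead-in.

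**Control.** Protocol 9.7.1 and SAP Section 3 use, for the MDS historical control, "a prior distribution of Beta(15,75) by discounting historical CR rate by half", citing AZA-001. Protocol 1.2.3 describes that trial's patients as intermediate-2 and high-risk MDS. The treatment prior, Beta(1,6), rests on 1 CR among 7 lead-in MDS patients.

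**The concern.** There are two separate problems.

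First, the CR row of Appendix 2 is a set of levels: hemoglobin at least 11 g/dL, neutrophils at least 1 x 10^9/L, platelets at least 100 x 10^9/L, no blood blasts and marrow blasts of 5% or less. It also asks for normal maturation, with persistent dysplasia to be noted. It contains no change from baseline and no upper limit on white cells. Removing the blast floor for CMML makes it possible to satisfy every numeric element before the first dose. SAP 6.1.1 adds no check.

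Second, Protocol 3.3 states the aim of the expansion as a CR rate reasonably better than that of historical azacitidine. If the cohort contains patients whom the control does not represent, the comparison mixes case-mix with drug effect. This can affect the futility decision as well as the reading of the final rate.

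**Working it through.** **1. Reproduce the plan's boundary.** Inputs from Protocol 9.7.1: treatment E ~ Beta(1+x, 6+n-x) after x CRs in n patients; control S ~ Beta(15,75); stop if Pr(E < S + 0.2) > 0.95. Numerical integration gives:

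- 2 of 10: 0.960, stop; 3 of 10: 0.882, continue.
- 4 of 17: just above 0.95, stop (the plan's own example); 5 of 17: 0.88, continue.
- 7 of 28: 0.951, stop; 8 of 28: 0.903, continue.

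Table 8 is reproduced at every n from 10 to 29. The maximum exact 95% CI width at n=30 is 0.374, as stated. The control prior also fits its source. Assuming 179 azacitidine patients (half of the 358), 0.17 x 179 = 30.4 CRs; halved, this is 15.2 CRs and 74.3 non-CRs. The prior mean is 15/90 = 16.7%.

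**2. Can a patient meet the numeric CR limits at screening and still be eligible?** Suppose the IPSS-R threshold (above 3 points) applies to the CMML and MDS/MPN-U bullets, which the text leaves unclear. By Appendix 10, CR-level hemoglobin, platelets and neutrophils all score 0, so karyotype and blasts must supply the points:

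- Blasts above 2% to below 5% (1) plus poor karyotype (3) = 4, Intermediate: eligible.
- Blasts of 2% or less (0) need very poor karyotype (4).
- Blasts of exactly 5% (2) need at least intermediate karyotype (2).

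So it is possible, but only in restricted combinations. It is not confined to CMML: the MDS cytopenia limit in Appendix 12 includes neutrophils below 1.8 x 10^9/L, while CR needs only 1.0. Each such patient adds 1/30 = 3.3 points at full enrollment.

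**3. Effect of case-mix on the futility rule.** The documents give no share f and no CR rate for these patients, so what follows is illustration. It uses exact binomial recursion through Table 8 and assumes independent patients, mature data and a look at every n from 10 to 29.

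Upward, starting from no gain over the control mean, with share f having a CR rate d points higher (added points = f x d):

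| f, d | Cohort CR | Escapes futility |
|---|---|---|
| none | 16.7% | 4% |
| 1/8, 20 | 16.7 + 2.5 = 19.2% | 8% |
| 1/3, 20 | 16.7 + 6.7 = 23.3% | 19% |

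The 1/8 is the only mix the documents show: 1 CMML beside 7 MDS patients in the lead-in.

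Downward, with a true rate of 37% (17% + 20 points) in MDS and a share that cannot reach CR:

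| Share | Cohort CR | Stopped for futility |
|---|---|---|
| 0 | 37% | 33% |
| 10% | 0.9 x 37 = 33.3% | 45% |
| 20% | 0.8 x 37 = 29.6% | 59% |

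**4. AML cohort.** Its control, Beta(23.5,97), comes from the trial described in Protocol 1.2.3: age 65 or over with more than 30% marrow blasts. The expansion takes patients from age 18 with AML by WHO 2016 and sets no 30% floor. The mismatch is of the same kind; its size cannot be computed from the documents.

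**The case against.** The strongest defense is that the gap is narrower than it looks.

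- A reader might infer that these patients have no response criteria at all. The documents do not support that. Protocol 2.4 assigns the Appendix 2 measures to the MDS cohort, the SAP footnote covers non-proliferative CMML, and the term MDS patients in 7.7.1 may mean the cohort. What remains is that proliferative CMML and MDS/MPN-U are nowhere named, and that the two footnotes differ. Version lag probably explains this: SAP Section 1 follows Amendments 5 and 6, while Amendment 7 added these patients.
- A reader might infer that CMML of any kind can enter. Criterion 2 requires an azacitidine indication. Under the EU indication described in Protocol 1.2.3 (non-proliferative CMML, 10-29% blasts), a patient could not have 5% or fewer blasts at entry. The limit depends on the label, however, and the US approval is described more broadly.
- The control mismatch is partial. Protocol 1.2.1 states more than 80% concordance of IPSS-R with IPSS, and 1.2.3 calls the lead-in population, which included non-proliferative CMML, aligned with AZA-001. The prior also halves the historical information.
- The control has one specified use, the futility rule. SAP 4.1 sets no formal hypothesis, and the final analysis is a proportion with an exact CI.
- CR in MDS must last 4 weeks and includes normal maturation. Both limit baseline credit, but neither excludes it: stable counts last, and persistent dysplasia is only noted.

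All of this lowers the likely size. None of it supplies a screening check or separates case-mix from drug effect.

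**Conclusion.** The point holds in limited form. Patients outside the control population enter the primary CR rate and the futility rule, and the CR definition allows an uncommon patient to qualify on the numeric elements before treatment, at 3.3 points each with n=30.

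A reader might go further and conclude that the MDS result will be inflated by a large part of the 20-point margin. The documents do not support that. They give neither the mix nor CR rates for CMML and MDS/MPN-U, and the bias may run either way, as the two tables show. Nor is the plan's arithmetic at fault, since Table 8 follows from its stated priors. The illustrated probabilities rest on the assumed f, d and unreachable shares, and on continuous looks.

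**What to change.** 1. **SAP 6.1.1.** In the MDS cohort, count CR only if at least one numeric Appendix 2 CR element (hemoglobin, neutrophils, platelets, blood blasts, marrow blasts) was abnormal at screening. Maturation should not serve as the qualifying element, because the criteria tolerate persistent dysplasia. Alternatively, report CR with and without patients who met all numeric elements at screening.
2. **SAP 8.2.1.** Add a descriptive CR rate with exact 95% CI in MDS-only patients, optionally limited to IPSS Intermediate-2/High re-derived from screening data. For AML, add the same in patients aged 65 or over with more than 30% blasts.
3. **Clarification.** Reconcile the protocol and SAP Appendix 2 footnotes, and state which criteria apply to CMML (proliferative or not) and to MDS/MPN-U.

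Cost: SAP wording and a short protocol clarification. Screening counts, marrow blasts and karyotype are already collected (Protocol Table 3, Appendix 8). Protocol Section 9 asks for an amendment if the primary endpoint definition undergoes a major modification; if the screening rule is judged to be one, the with-and-without report avoids it. The subsets will be smaller and less precise: the maximum exact 95% CI width is about 0.46 at n=20 and 0.52 at n=15, against 0.374 at n=30.
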